There has been no additional adaptation of the Kitbag itself from the school setting but the support is tailored to the social work setting, focusing on the relationship-based and reflective practice skills of the social workers and their role in leading the shift in practice within their teams.

As mentioned above, we expect that the version of the programme trialled will involve considerably more use of the Kitbag Online than in non-Covid-19 times. We attempt to address the generalisability of the findings in the implementation and process evaluation (please see below).

Logic model

* indicates outcomes that will be measured.

Impact Evaluation

Research questions

Primary research questions

Child outcomes:

- Primary outcome 1: What is the impact of the “Putting the Kitbags to work” programme on the number of **escalations and de-escalations** of eligible children supported by social workers? The comparison is between eligible children supported by social workers in teams randomly allocated to the intervention arm compared with eligible children supported by social workers in teams randomly allocated to the control arm within the intervention period.
- Secondary outcome 1: What is the impact of the “Putting the Kitbags to work” programme on the **behaviour** of eligible children supported by social workers? The comparison is between eligible children supported by social workers in teams randomly allocated to the intervention arm compared with eligible children supported by social workers in teams randomly allocated to the control arm. The outcome will be measured by the total difficulties score of the Strengths and Difficulties Questionnaire. The population will be restricted to children who’ve been looked after continuously for 12 months or more whose SDQ has been assessed from T4 - T12.

Social worker outcomes:

[figure not shown]
- Secondary outcome 2: What is the impact of the “Putting the Kitbags to work” programme on the **self-efficacy** (as measured by the competency subscale of the Work-Related Basic Needs Satisfaction scale) of social workers and family support workers in teams randomly allocated to the intervention arm compared with social workers and family support workers in teams randomly allocated to the control arm? The outcome will be measured at month 6 and month 13 after intervention began.

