Since the intervention is allocated by team, we define eligibility criteria for teams: statutory teams who we would typically expect to conduct longer term (4+ months) work with children and young people to allow for the minimum number of sessions with a Kitbag. This includes safeguarding teams who work with child and young people who are subject to a child in need (CIN) plan or a child protection plan (CPP), teams that work with children who are looked after (CLA) or teams who work with children with disabilities. Please see Table 1 for the number of eligible teams per local authority. As different local authorities have slightly different names for each team, we've included the type of team in brackets. The teams we have determined are not eligible to participate therefore, are MASH / front door, assessment, early help, youth justice and leaving care teams as they do less of the longer term direct work. Please see Table 2 for the number of social workers, family support workers and foster carers.

Table 1: Eligible teams within each local authority

Local authority	Eligible teams
Bexley	Family support and child protection teams (North, East, Central and South, South West) (4 CIN / CPP teams) Looked After Children team (1, 2, 3) (3 CLA teams) Children with Disabilities team (1, 2) (2 Children with disabilities teams) Total: 9 eligible teams
Haringey	Children in Care team (1, 2) (2 CLA team) Disabled Children's team (1, 2) (2 Children with disabilities teams) Safeguarding and Support team (1-6) (6 CIN / CPP teams) No Recourse to Public Funds team (1 CIN / CPP teams) Total: 11 eligible teams
Oxfordshire	Children's Disability Teams (North, South, City) (3 Children with disabilities teams) Family Solutions Plus Teams (North 1-6, Central 1-5, South 1-6) (17 CIN / CPP teams) Rosehill Statutory Teams (1, 2) (2 CIN / CPP teams) Unaccompanied Children (1 CLA team) Children in Care (North 1, North 2, South 1, South 2, Central 1a, Central 1b, Central 2) (7 CLA teams) Total: 30 eligible teams
Warwickshire	Safeguarding and support (Bedworth and North Warwickshire, Nuneaton, Rugby, Stratford, Warwick) (5 CIN / CPP teams) Children in Care aged 14-18 (1 CLA teams) Strengthening Families (1 CIN / CPP team) Children with Disabilities (safeguarding and support hub, children in need hub, strengthening families hub) (3 Children with disabilities teams) Total: 10 eligible teams
Total	60

Social workers and family support workers

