If the sample is imbalanced with respect to team type (CIN / CP, CLA, children with disabilities) within the local authority, we will re-randomise (setting a new seed). We take imbalance to be the proportion of teams of that type within the local authority assigned to the intervention to be greater than 0.75 or less than 0.25 (i.e. $\frac{3}{4}$ or $\frac{1}{4}$ teams) except where there is only one team of that type in the local authority.

We will also report the mean proportion of social workers to family support workers, and the mean proportion of permanent staff to agency staff, by treatment allocation but will not re-randomise if there is imbalance in treatment allocation on these variables. With a relatively small number of teams to allocate, we have decided to prioritise team type (within the local authority) to enable us to compare the impact of the programme on these subgroups.

Data collection

We have several data collection methods:

Impact evaluation

- Children and young people:
 - administrative data to measure children's social care involvement
- Social workers:
 - online survey to measure self-efficacy, stress
 - administrative data to measure sickness absence
- Foster/kinship carers:
 - online survey to measure self-efficacy

⁷ Due to a delay of the required data from Oxfordshire County Council, the randomisation was conducted for the three other local authorities first, and the teams from Oxfordshire County Council were allocated separately.

Sample size / MDES calculations

		MDES (Proportion of a Standard Deviation)
MDES		0.127
Proportion of variance in child's outcome explained by:	Child covariates (including baseline measure)	0.8
	Social Worker team covariates	0.1 (3 covariates)
Intraclass correlations (ICCs)	Team	0.03
Alpha		0.05
Power		0.8
One-sided or two-sided?		Two-sided
Level of intervention clustering		Social worker team
Average cluster size		150 children in each team
Sample Size (children)	Intervention	4500
	Control	4500
	Total	9000
Sample Size (teams)	Intervention	30 (15 per local authority)
	Control	30 (15 per local authority)
	Total	60

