For child outcomes:

$$Y_{ict13} = \beta_0 + \beta_1 D_c + \beta_{2:4} A_c' + \beta_5 Y_{ict0} + \beta_{6:k+6} X_i' + \epsilon_c$$

Where all is defined as above.

Exploratory Analysis

Site effects

In line with WWCS statistical guidance, we account for potential site effects by including a site (local authority) fixed effect and interaction terms between the treatment and sites. The coefficients on these interaction terms can be interpreted as the difference in intervention group mean for that site and the overall treatment mean. The trial is not powered to detect site-specific effects, and so we report only the direction of the site-dosage effects and the standard errors as exploratory analysis. The interpretation of the coefficient on the treatment variable is the simple average between sites (rather than an average weighted by sample size at each site).

Site effects will be tested for all outcomes. The regression specifications will follow the above with the addition of a vector of interaction terms between treatment and local authority fixed effects. E.g. for social workers and foster carer outcomes:

$$Y_{ict13} = \beta_0 + \beta_1 D_c + \beta_{2:4} A_c' + \beta_{5:8} D_c * A_c' + \beta_9 Y_{ict0} + \beta_{9:k+9} X_i' + \beta_{k+9:k+14} M_c' + \epsilon_c$$

Where:

- $D_c * A_c'$ is a vector of interaction terms between treatment and local authority fixed effects.
- And all else is defined as above

Dosage

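### Warwickshire's single looked-after team has no comparator in its own stratum, so the planned SDQ site effect and four-site average are either not estimable or mix team types

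*Protocol*

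**What the plan says.** - **Teams.** In Participants – Teams, Table 1, the only CLA entry for Warwickshire is "Children in Care aged 14-18 (1 CLA teams", within "Total: 10 eligible teams". The other nine are six CIN/CPP teams and three disability teams ("Children with Disabilities (safeguarding and support hub, children in need hub, strengthening families hub) (3 Children with disabilities teams"). Bexley has three CLA teams ("Looked After Children team (1, 2, 3) (3 CLA teams"), Haringey two and Oxfordshire eight.
- **Randomisation.** Teams are randomised within authority and team type. The re-randomisation rule for lopsided strata applies "except where there is only one team of that type in the local authority".
- **SDQ population.** Research questions, Secondary outcome 1, restricts the analysis to children "looked after continuously for 12 months or more whose SDQ has been assessed from T4 - T12". This is a condition on the child, not on the type of team holding the case.
- **Main model.** Analysis plan – Covariates has site fixed effects and no site-by-treatment terms. Team type is listed among the team-level covariates, but the child-outcome equation in Regression specification omits the team-level term that the staff and carer equation contains.
- **Site model.** Exploratory Analysis – Site effects adds site-by-treatment terms and states "Site effects will be tested for all outcomes". Direction and standard errors are to be reported, and the treatment coefficient "is the simple average between sites (rather than an average weighted by sample size at each site".

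**The concern.** The SDQ outcome concerns looked-after children, and in Warwickshire the one team dedicated to them is, by design, all intervention or all control. No comparison of like teams exists within that stratum. The site analysis nevertheless promises a Warwickshire SDQ direction and standard error, and a four-site average in which each authority counts equally.

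At stake is whether those outputs mean what the protocol says they mean. Depending on where Warwickshire's long-term looked-after children are held, they either do not exist or partly compare a care team for ages 14–18 with safeguarding or disability teams. A reader in Warwickshire could take such a result as local evidence on Kitbag.

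**Working it through.** **Step 1. Recount of Table 1.**

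| Authority | CIN/CPP | CLA | Disability | Total |
|---|---|---|---|---|
| Bexley | 4 | 3 | 2 | 9 |
| Haringey | 7 | 2 | 2 | 11 |
| Oxfordshire | 19 | 8 | 3 | 30 |
| Warwickshire | 6 | 1 | 3 | 10 |
| Total | 36 | 14 | 10 | 60 |

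The table's own totals are reproduced. Warwickshire has 1/14 = 7% of CLA teams.

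**Step 2. Only CLA teams hold SDQ-eligible children.** The site model has an intercept, a treatment term, 3 site terms and 3 interactions, so 8 parameters. That equals one mean per authority and arm. One Warwickshire cell is empty, so the rank is 7. The effects in Bexley, Haringey and Oxfordshire are estimable; the Warwickshire effect is not. The simple average, (d_B + d_H + d_O + d_W)/4, contains d_W and so is not estimable either.

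In the main fixed-effects model, with teams of equal size, each site's weight is proportional to n1·n0/(n1 + n0). The splits below are assumed, within the balance rule:

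- Bexley 2:1 gives 0.667
- Haringey 1:1 gives 0.5
- Oxfordshire 4:4 gives 2
- Warwickshire 1:0 gives 0

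The sum is 3.167, so the weights are 0.21, 0.16, 0.63 and 0. The main SDQ estimate then rests on three authorities without saying so.

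**Step 3. Other Warwickshire teams also hold such children.** Suppose one further treated and one further control team do (assumption). The rank is now 8 and Warwickshire carries exactly 0.25 of the simple average. In the main model its split of 2:1 gives 0.667/3.833 = 0.17.

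With no team-type term, any SDQ gap between the CLA team and the others enters the Warwickshire contrast. For an assumed gap of 0.3 SD, the site average moves by at most 0.3/4 = 0.075 SD. The sign depends on the arm drawn for the CLA team. That draw is random, so the mean shift over allocations is zero.

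**Step 4. Standard error in the Step 3 case.** Simulation assumptions: 120 SDQ children in the Warwickshire CLA team, 50 in each other CLA team, 20%, 40% or 60% of Warwickshire SDQ children in its nine other teams, ICC 0.03, allocation within strata, no covariates. Results for the Warwickshire effect with no true effect and no gap:

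| Share in other teams | True SD | Mean clustered SE | Shortfall, 1 − SE/SD |
|---|---|---|---|
| 20% | 0.33 | 0.24 | 27% |
| 40% | 0.23 | 0.17 | 26% |
| 60% | 0.18 | 0.14 | 22% |

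Across repeated runs of this set-up, |t| > 1.96 occurred in 16–22% of null trials, and in 21–34% when the 0.3 SD gap was added. With a team-type term it occurred in 12–13%, with or without the gap. The term therefore removes the gap's contribution; the remaining excess over 5% comes from having few clusters.

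**Step 5. Haringey.** The balance rule forces its two CLA teams to split 1:1. If they alone hold its SDQ-eligible children, each arm is one team. With only site and site-by-treatment terms, residuals sum to zero within each site-by-arm cell, which here is each cluster. The team-clustered standard error of the Haringey effect is then exactly zero.

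**The case against.** **A stronger reading does not hold.** A reader might infer that Warwickshire has no randomised comparator at all and still carries a quarter of the average. The protocol does not support this. SDQ eligibility follows the child's status, nine other Warwickshire teams are randomised, and the protocol does not say which teams hold children looked after for 12 months or more. Table 2 gives Warwickshire 148 of the 424 intervention-arm carers (35%), the most of any authority, but this does not settle the matter. The two halves also exclude each other: with no comparator the effect has no weight because it cannot be estimated (Step 2); with comparators it has weight one quarter (Step 3).

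**Nor is the result biased in one direction.** The CLA team's own arm is randomised, so a difference between team types adds variance.

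**The planned covariates help.** Previous SDQ, age group, disability and type of involvement are in the child model and the simulation left them out, so its figures are illustrative. They may narrow the gap, but the 12–17 age band does not separate children of 14 and over from those of 12–13, and no covariate supplies a second CLA team.

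**The scope is limited.** The site analysis is labelled exploratory and unpowered, and the main SDQ model has no interactions. This stands and lowers the importance of the point. A statistical analysis plan may deal with one-armed sites, but the protocol itself fixes an all-outcomes site analysis and an interpretation of its coefficient that Table 1 may not support.

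**Conclusion.** The point holds for the exploratory SDQ site analysis. Warwickshire's CLA stratum is one-armed whatever the draw. If it is the only source of SDQ data there, the Warwickshire effect and the four-site average are not estimable, and the main estimate comes from three authorities. This follows from the design alone. If other Warwickshire teams contribute, the effect is estimable and carries a quarter of the average, but mixes team types. Its clustered standard error is then about 25% too small under the stated team sizes and ICC, without covariates.

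The consequence is extra chance variation and overstated precision in a secondary, exploratory output. The documents do not support a claim of systematic bias, or of material damage to the main SDQ analysis. The 0.3 SD gap and the resulting 0.075 SD are assumptions for scale only.

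**What to change.** 1. Add team type, which is a randomisation factor and already a listed covariate, to the child-outcome equations. This removes the team-type gap in the Step 3 case. It cannot create a Warwickshire effect in the Step 2 case.
2. For the SDQ, report a site-specific effect, and include a site in the simple average, only where both arms contain SDQ-eligible children within at least one team type. State which sites the average covers.
3. Do not report team-clustered site-specific standard errors where an arm has a single team. This also applies to Haringey if its two CLA teams alone hold SDQ-eligible children. A rule requiring at least two CLA teams would not be enough, because it would keep that case.
4. State which authorities contribute to the main SDQ estimate.

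The cost is wording, one model term and a count of SDQ-eligible children by team. The SDQ site average may no longer speak for every authority, and precision falls slightly.

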Carers (including kinship and foster carers) will be identified and recruited through the same mechanisms as social workers/family support workers. The birth parents of children in care will not be included as participants.

English as an additional language

In order to complete their working responsibilities, we assume that social workers and most foster carers have a level of English language comprehension that would allow them to fully participate in the evaluation if they wish to. Where this is not the case (e.g. EAL is a bit more common for foster carers who foster unaccompanied asylum seekers), we shall ask social workers if they can support the foster carer to answer the questions.

Randomisation

Randomisation will take place at the level of the team in a two-armed clustered trial, stratified by local authority and the team type (CIN / CP; CLA; children with disabilities). We will

⁶ Department for Education (2019) Characteristics of children in need tables: 2019, Table B4. <https://www.gov.uk/government/statistics/characteristics-of-children-in-need-2018-to-2019>

randomise at the social worker team level for three reasons. Firstly, the randomisation is not at the level of the child or young person because the resource is not given to the child or young person but used in direct work with the child and family by the social worker, family support worker, or foster carer. Secondly, the randomisation is not at the social worker level because social workers in the same team would be expected to discuss practice and there would be a risk of contamination. Thirdly, an element of the intervention is the use of Kitbag by social workers and family support workers in their team setting, for example in team meetings. While contamination may still be possible cross-team (or even cross-organisation), we believe that this is sufficiently limited that team-level randomisation remains most appropriate, when considering trade-offs with statistical power.

Each social worker or family support worker gets their own Kitbag if they are in one of the treated teams. Each in-house foster carer or kinship carer who is caring for a child or young person supported by a social worker or family support worker in a treated team will receive a Kitbag.

We will stratify at the local authority/team type level to ensure balance on the level of children's social care involvement that the teams focus on⁷.

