- for social workers and family support workers: the social worker or family support worker was a member of a team assigned to the intervention at point of randomisation and 0 else;
- for foster / kinship carers: the carer cares for a child or young person whose case is held at the point the foster carer enters the sample, by a social worker who is a member of a team assigned to the intervention at point of randomisation and 0 otherwise.

Although there is some turnover of social workers, family support workers and foster carers, about 80% of those at T0 (April 2021) will still be working with the local authority at T13 (May 2022), and so 80% will have received the full 12 months of the intervention. Binarising the treatment seems a reasonable proxy in this case.

For the outcomes relating to children, treatment is coded as a binary variable. When children enter the sample, at either the point of randomisation, or the point they become eligible (e.g. their case opens and meets other criteria) they will be allocated to treatment if the team of their allocated social worker was randomised to treatment.

Covariates

Including control variables increases the precision of the estimate. In each regression, we control for a number of relevant covariates. We outline different categories of covariates below.

Site effects

We include site fixed effects but not site-treatment interaction terms.

Previous outcome measures

We control for the previous measurements of the outcome variable where data is available. For the survey-based measures for social workers, family support workers and foster carers, the same measures will be asked at T6 (October 2021) and T13 (May 2022), and for administrative data we expect previous values to be available. For the outcomes of the CYP and parents / carers (including kinship carers), the previous measure of the outcome will be at T0 (April 2021) or when they entered services if they entered services after T0 (April 2021).

Other covariates

For CYP outcomes (primary outcome i) and secondary outcome i)), we include the following vector of individual-level covariates:

- gender (coded as male, female, or other/missing)
- age group (4-11, 12-17, 18 years, or missing with 4-11 as the reference category)
- ethnicity (Asian / Asian British, Black / African / Caribbean / Black British, Mixed / Multiple ethnic groups, Other ethnic group, White, missing; with the majority group as the reference category)

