- disability status (Yes, No, Don't know/missing with No as the reference category)
- most recent type of CSC intervention (coded as :
 - Child in Need
 - Child Protection Plan
 - Looked After - LA fostering / kinship care
 - Looked After - IFA / other LA fostering other placement type
 - missing;
 - with Child in Need as the reference category)

- unaccompanied asylum seeking child (yes, no, or missing with no as the reference category)
- if possible, whether their social worker has changed over the intervention period (yes, no, missing with no as the reference category)
- for the primary outcome 1-3 only, the number of status changes within the intervention period (numeric: as per the children's social care interaction outcome variable)

For social worker and family support worker outcomes, we include the following individual-level covariates:

- gender (coded as male, female, or other/missing),
- role (social worker, family support worker, or missing; with social worker as the reference category)
- contract type (permanent, agency or missing; with permanent as the reference category)
- the number of years experience (Associated and Supported Year in Employment / years<1, 1≤ years<4, 4≤years<9, 9years<15, ≥15 with ASYE as the reference category)

We include the following team-level characteristics (measured at T0):

- team type as categorised in Table 1 above (CINP / CPP, CLA, children with disabilities with CINP / CPP as the reference category)
- team size (numeric)
- percentage social worker or family support worker (numeric)
- percentage permanent or agency workers (numeric)

For foster carers (where we can match the data):

- gender (coded as male, female or other/missing)
- employer (LA foster carer, employed by an independent fostering agency or another local authority, or missing; with LA foster carer as the reference category)
- number of years experience (numeric)

Where the foster carer answering the survey is different between pre and post intervention data collection (e.g. the foster carer who answered at baseline isn't available or no longer fosters the child), the post data will be collected from the available foster carer and their pre data will be recorded as missing. The data collected from the foster carer who answered at the pre data collection point will be discarded (we won't impute their outcome data).

Please see the regression specification.

Standard errors

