Children are clustered into sibling groups, households (e.g. with other children in foster care) and caseloads (i.e. a group of children have the same social worker) and social worker teams. Because of this clustering, observations within one group (sibling group, household etc) may be more similar with each other on various characteristics compared with observations in other groups violating the assumption of independence. When data is structured in this way, the estimation of the treatment effect remains unbiased but the standard errors may be misspecified, leading to problems with inference. To correct for this, standard errors will be clustered at the level of randomisation, the social worker team level, in line with WWCS statistical guidance. This also accounts for correlations between observations at lower levels of nesting.

Handling non-compliance

If CYP are transferred to another team (e.g. due to a change of status), it is possible that the team to which they are transferred was ineligible for participating in the programme or had a different intervention / comparator group allocation. If a social worker or family support worker changes teams, it is possible that their new team had a different intervention/ comparator allocation. For all our analysis, we will conduct intention to treat analysis where a CYP is considered as treated if they are / were supported by a social worker who is a member of an intervention team at the point they entered the sample (either at randomisation or when their case started), irrespective of their use of Kitbag.

Multiple Comparison Adjustments

We will adjust for multiple comparisons within the secondary outcomes using Hochberg's step-up procedure, as per WWCS statistical guidance.

Regression specification

For social workers, family support workers and foster carer outcomes:

$$Y_{ict13} = \beta_0 + \beta_1 D_c + \beta_{2:4} A_c' + \beta_5 Y_{ict0} + \beta_{6:k+6} X_i' + \beta_{k+6:k+11} M_c' + \epsilon_c$$

Where:

- Y_{ict13} is the dependent variable for individual i , team c at the end of the trial, $t13$. β_0 is the intercept
- D_c is the treatment variable
- A_c is a vector of the local authority fixed effects
- Y_{ict0} is the "pre" outcome of individual i in team c , at their "pre" data collection point, $t0$
- X_i' is an $N \times k$ matrix of characteristics of individual i
- M_c' is an $N \times 5$ matrix of characteristics of team c
- ϵ_c is the error term clustered at the team level c

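### Team type is a stratifier and team covariates are counted in the power table, but the child-outcome model has no team-level term: a modest loss of precision, not bias

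*Protocol*

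**What the plan says.** - **Randomisation.** Teams are allocated "stratified by local authority and the team type (CIN / CP; CLA; children with disabilities"). The allocation is redrawn if the share of a team type assigned to the intervention within an authority falls outside 0.25 to 0.75, and the protocol says that it gave team type priority.
- **Other covariates.** For child outcomes, "we include the following vector of individual-level covariates": gender, age group, ethnicity, disability status, "most recent type of CSC intervention (coded as" child in need, child protection plan and two looked-after categories), unaccompanied asylum-seeking status, and change of social worker if available. After the staff list comes "We include the following team-level characteristics (measured at T0"), headed by team type.
- **Regression specification.** The staff and carer equation carries a term that "is an $N \times 5$ matrix of characteristics of team c". The equation introduced by "For child outcomes" has treatment and local authority effects and then ends "\beta_5 Y_{ict0} + \beta_{6:k+6} X_i' + \epsilon_c". It has no team matrix.
- **Sample size / MDES calculations.** The table is computed for the child outcome. Its row "Social Worker team covariates" enters a proportion of variance explained of 0.1 from three covariates, and the stated MDES is 0.127.

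**The concern.** A factor used to restrict the randomisation should normally be in the analysis model. Stratification makes the treatment estimate less variable. A model without the stratifier leaves that factor's variance in the residual, so the standard error is too large on average and the test rejects too rarely.

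The team level is where this counts. With about 150 children per team, nearly all the modelled error variance lies between teams. Team type is also a plausible source of it, because the primary outcome sums steps between case closed, child in need, child protection and care. A child's starting level limits which moves are possible, and team type follows that level.

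The power table and the model also disagree: the table counts a gain from team covariates that the printed child model does not use.

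**Working it through.** **Inputs (Sample size / MDES table and the text below it).** K = 4 authorities, J = 15 teams on average (60 in all), n = 150 children per team, half the teams treated (P = 0.5), ICC 0.03, child-level R² 0.8, team-level R² 0.1 with g = 3 covariates, two-sided alpha 0.05, power 0.80. The design is the three-level blocked cluster design with authorities as fixed blocks.

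**Formula.** MDES = M × SE, where

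- SE² = ICC(1 − R²team)/(P(1−P)JK) + (1 − ICC)(1 − R²child)/(P(1−P)JKn)
- M = t(0.975, df) + t(0.80, df), with df = K(J − 2) − g
- P(1−P)JK = 0.25 × 60 = 15

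**1. The table as printed, with team covariates.**
- Between-team part: 0.03 × 0.9 / 15 = 0.001800
- Within-team part: 0.97 × 0.2 / (15 × 150) = 0.000086
- SE = √0.001886 = 0.0434; df = 49; M = 2.859
- MDES = **0.124**, about 2% below the stated 0.127. The stated figure is therefore matched only approximately, but the comparison with step 2 does not depend on that.
- The between-team share of SE² is 0.001800/0.001886 = 95%.

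**2. The child model as printed, taking the team R² as zero (worst case).**
- Between-team part: 0.03 / 15 = 0.002000; the within-team part is unchanged
- SE = √0.002086 = 0.0457; df = 52; M = 2.855
- MDES = **0.130**, about 5% above 0.124

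**3. Power from the noncentral t distribution.**

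| True effect (SD) | With team covariates | Without |
|---|---|---|
| 0.127 | 81.8% | 77.9% |
| 0.124 | 80.0% | 76.0% |

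Without the covariates, about 66 teams instead of 60 would be needed for an MDES of 0.124.

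**4. Sensitivity.** The relative loss is 4 to 5% for child-level R² from 0 to 0.8 (for example 0.135 to 0.141 at R² = 0) and about 5% for ICC from 0.01 to 0.10.

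**5. Check by simulation.** The 60 teams of Table 1 were allocated at random within authority-by-type strata. A team-level model with authority effects was fitted with and without type dummies, using robust standard errors and t(59), for a true effect of 0.127 SD. The shares below are of between-team variance; the absorbed fraction is an assumption.

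| Team type explains | Absorbed by child covariates | Power without type | Power with type | Type I error without type |
|---|---|---|---|---|
| 10% (table's figure) | none | about 79% | about 82% | 4 to 5% |
| 10% | half | about 80–81% | about 82% | just under 5% |
| 30% (not in the protocol) | none | about 81% | about 90% | 2 to 3% |
| 30% (not in the protocol) | half | about 85% | about 89% | just under 4% |

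**The case against.** The best defence is that team type already enters the child model by proxy. The protocol says it stratifies to balance the level of social care involvement on which teams focus. The child model adjusts for that level child by child, and adds disability and unaccompanied-child status. In an uncentred OLS model these covariates, and the previous outcome, also absorb differences between teams whose case mix differs. This stands. It makes 0.130 a worst case and not the MDES of the printed model, and at a 10% share with half absorbed the loss is about one point of power. The proxies are still partial: a child's disability status does not establish that a disability team holds the case, and no listed child covariate is the stratum.

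The sentence introducing the team-level covariates is also not expressly confined to staff outcomes, so the gap may be one of drafting. That is possible, but the child equation contradicts it, and saying that all is defined as above adds no term. The two places need reconciling on either reading.

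Finally, the R² inputs were justified for SDQ scores and not for status changes. That is fair, and it makes the absolute figures illustrative for the present primary outcome.

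A reader might infer that the primary analysis ignores half the stratification and so runs at a type I error below 3%, with nine or so points of power lost. That needs team type to explain about 30% of between-team variance with nothing absorbed by child covariates. The protocol credits 10%, for three team covariates together.

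**Conclusion.** The point holds, at modest size. The child-outcome model omits a stratification factor, and every team covariate that the power table counts. On the table's inputs the worst-case cost is an MDES of 0.130 against 0.124 and about four points of power at 0.127 SD (78% against 82%), with a type I error slightly under 5%. The loss shrinks as the child-level proxies absorb the team-type effect, and grows only if team type explains more than 10% of between-team variance.

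These figures assume equal teams of 150, ICC 0.03 and the table's R² values. A reader might also infer a biased treatment effect; the documents do not support this, since allocation is random within strata and the error is in the conservative direction. The change should be made because it is nearly free and makes the analysis match the design and the power calculation.

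**What to change.** 1. Add team type to the child-outcome equation for the primary outcome and the SDQ outcome. Either of two forms will do:
   - two team-type dummies beside the authority effects, costing two degrees of freedom; or
   - authority-by-type strata. Table 1 gives 12 strata; pooling the single-team stratum (Warwickshire, children in care) leaves 11, which costs 11 − 4 = 7 degrees of freedom more than the authority effects alone.
2. Carry the same term into the exploratory child models (site, dosage, level of involvement, age, workload).
3. State in the covariate section which outcomes the team-level list serves, so that it agrees with the equations, and align the number of team covariates in the power table (three) with the team matrix (five columns).
4. If team covariates are deliberately left out of the child model, set the team R² to zero and restate the MDES, about 0.130 on the present inputs.

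The cost is a line in the specification. Team type is already known from Table 1, so no new data are needed.
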